### **Modification History**

Unique Identifier for Version	Date of IAP Version	Author	Changes from the Previous Version
1.0	29 JUN 2020		First version
1.1	25 OCT 2021		Protocol amendment integrated including 2 interim analyses Removal of Screening Log reference and external source data as not feasible to collect. Added list of outputs included in each interim analysis
1.2	11 NOV 2021		Section 9.5 updated adding table describing windowing
2.0	17 NOV 2021		Section 9.5 updated removing windowing for primary and secondary endpoint

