## 9.5 Windowing and Unscheduled Visits

As this is a non-interventional study, study assessments are part of the routine practice and related data will be collected during the visits in line with the Summary of Product Characteristics and as clinically indicated. Patients will attend the sites as per routine practice at the discretion of the treating physician. Therefore, the timing of the visits is an approximation.

The first visit will be the Baseline visit. Patients who meet all eligibility criteria and who sign the Informed Consent Form (ICF) can be enrolled in the study. Inclusion can occur at the time point of treatment prescription with Cladribine tablets up until the second treatment week of the first treatment year. Baseline data will be collected at the time of the visit.

In addition to the baseline data, data collection is planned at 4 supplementary visits according to routine practice: at months 6 (Visit 1), 12 (Visit 2), 18 (Visit 3) and 24 approximately (Visit 4).

Apart from Baseline visit, PROs assessments will be derived considering a 6 months ( $\pm$  30 days) frequency and will be calculated using study day as shown in table below:

Visit Name	Derivation
Baseline	Baseline visit a
Months 6 (Visit 1)	150 days ≤ STUDY DAY ≤ 210 days
Months 12 (Visit 2)	335 days ≤ STUDY DAY ≤ 395 days
Months 18 (Visit 3)	510 days ≤ STUDY DAY ≤ 570 days
Months 24 (Visit 4)	700 days ≤ STUDY DAY ≤ 760 days

<sup>a Baseline visits will not be remapped as the starting of the observation and will be assigned as per eCRF visit.

Out of windows data will be included in a sensitivity analysis for HRQoL.

As per the study design, the definition of unscheduled visits does not exist. According to the instructions provided to the sites, when more than 1 appointment occurs within a time-period (e.g. 6-Months), only the appointment closer to the upper limit of that visit will be recorded in the eCRF.

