### 10.2 Protocol Deviations/Exclusion from Analysis Populations

## **10.2.1 Important Protocol Deviations**

Important protocol deviations (IPDs) are protocol deviations that might significantly affect the completeness, accuracy, and/or reliability of the study data or that might significantly affect a participant's rights, safety, or well-being. Since this is a non-interventional study and all procedures will be performed as per clinical practice, deviation from the expected schedule of assessments as presented in the Protocol Section 9.2.4 are not considered IPDs.

The list of potential protocol deviations is available at Appendix 18.1 according to the study Protocol Deviation Plan version 1.0 from 21 November 2019.

A frequency table with all IPDs based on FAS will be presented.

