# 14.1.1 Primary Objective: Derivation and analysis of the Primary Outcome ARR

#### **Derivations**

Pre-baseline ARR will be defined as a total number of relapses reported in the last 12 months prior to Cladribine treatment as collected in the "12 Month Historical MS Data".

Twelve month period before the End of Study follow-up (2 years) ARR will be calculated as the sum of the number of MS relapses reported at Visit 3 and Visit 4 divided by the number of days between Visit 4 date and Visit 2 date and multiplied by 365.25. If a patient discontinues the study prior to Visit 4, it will be set to missing and excluded from the primary analysis.

For other study visits, ARR will be calculated similarly including data from the last 2 visits, except for ARR at Visit 1 for which only the last 6-month data will be included, and the annualized rate will be adjusted as per the formula described above. For ARR at Visit 1 and Visit 2, Cladribine start date will be used as the date to calculate the number of days elapsed.

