#### **Analysis methods**

No missing data imputation will be performed. Patients with missing data at one or both time points will not be included in the analysis. A one-way Repeated Measures Analysis of Variance (ANOVA) will be used to compare the differences between pre and post-baseline ARR if the data is normally distributed. The two-tailed test hypothesis for the primary outcome is H0: ARR mean difference between pre and post-baseline ARR is 0 vs H1: ARR mean difference between pre and post-baseline is different than 0. Statistical significance will be assessed at the 5% level.

In case the data is not normally distributed, Wilcoxon signed-rank test will be used instead. The Shapiro-Wilk test will be used to test for data normality.

Main primary outcome table will include only summary statistics for pre-baseline and post-baseline ARR data including the p-value for the statistical test result described above. Additionally, a table includes ARR summary statistics by visit, including ARR at each visit and absolute and relative change from baseline. For a change from baseline, 95% CIs for the difference will be presented together with summary statistics. These CIs will be included as a descriptive measure of effect and no inferences will be made.

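### A patient seen at Visit 4 but with no Visit 2 falls out of the primary ARR comparison, and the SAP has no rule for an absent Visit 3 count

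*SAP*

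**What the plan says.** SAP 14.1.1 (Derivations) takes as the numerator of the year-2 ARR the "sum of the number of MS relapses reported at Visit 3 and Visit 4". That count is turned into a yearly rate using the time since Visit 2; in the SAP's words it is "divided by the number of days between Visit 4 date and Visit 2 date and multiplied by 365.25". The section names one situation in which the value is missing: "If a patient discontinues the study prior to Visit 4, it will be set to missing and excluded from the primary analysis". Under Analysis methods the same section adds "No missing data imputation will be performed" and, on incomplete pairs, "Patients with missing data at one or both time points will not be included in the analysis".

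Attendance is not fixed by the study. SAP 9.5 states: "Patients will attend the sites as per routine practice at the discretion of the treating physician". SAP 10.2.1 says that "deviation from the expected schedule of assessments as presented in the Protocol Section 9.2.4 are not considered IPDs". The visit windows now in SAP 9.5 apply to patient-reported outcomes only; the Modification History for version 2.0 records "Section 9.5 updated removing windowing for primary and secondary endpoint". SAP 9.5 tells sites which appointment to record when several fall in one period, but gives no rule for a period with none.

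Protocol 9.2.4 asks at each of Visits 1 to 4 for a running total of relapses since study entry. SAP 14.1.2 adds two sensitivity analyses, last observation carried forward (LOCF) and baseline observation carried forward (BOCF), described as supportive.

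**The concern.** The formula needs three records: the Visit 2 date, the Visit 3 count and the Visit 4 count. The missing-data rule addresses only patients who leave before Visit 4. In a study without mandated visits, some patients will plausibly be followed to month 24 with an earlier visit unrecorded, and the SAP does not say what happens to them.

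The consequences fall on the only confirmatory comparison (SAP 9). Patients with complete follow-up can be lost because of how the rate is written, not because their relapse history is unknown. Where Visit 3 is absent, two programmers could follow the text faithfully and obtain different primary results from the same data.

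**Working it through.** **Inputs.** The formula and exclusion rules are from SAP 14.1.1. The planned 242 patients are from protocol 9.5; the assumptions behind that number are redacted, so it cannot be reproduced and is not disputed here. The frequency p of a missed visit is not in the documents and is assumed to be 5%, 10% or 15%.

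**Step 1: apply the formula to each pattern.** Year-2 ARR = (R3 + R4) / (date of Visit 4 − date of Visit 2) × 365.25.

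- *Visit 2 absent, Visit 4 attended.* There is no Visit 2 date, no window rule that assigns another contact to Visit 2, and no imputation. The denominator is undefined, the ARR is missing and the patient is excluded.
- *Visit 3 absent, Visits 2 and 4 attended.* The denominator is defined. With Visit 2 on day 365 and Visit 4 on day 730 it is 730 − 365 = 365 days. Only the term R3 is absent, and the SAP does not say what then happens to the sum.

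**Step 2: a worked patient with Visit 3 absent.** Suppose one relapse in year 1 and two in year 2, so that the running totals at Visits 2, 3 and 4 would be 1, 2 and 3. The true year-2 ARR is 2/365 × 365.25 = 2.00.

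| Reading of the data and the formula | Year-2 ARR |
|---|---|
| An absent R3 voids the sum | missing, patient excluded |
| Counts run from the last attended visit, R4 = 2 | 2/365 × 365.25 = 2.00 |
| Running totals, Visit 4 total minus Visit 2 total = 3 − 1 | 2/365 × 365.25 = 2.00 |
| Running totals, R3 left out, R4 = 3 used as it stands | 3/365 × 365.25 = 3.00 |

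The same data can therefore give an exclusion, the right value or a wrong one. The type of count matters even with full attendance: if running totals were entered in the SAP formula, R3 + R4 = 2 + 3 = 5 and the ARR would be 5.00. The formula fits per-interval counts, whereas protocol 9.2.4 describes running totals.

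**Step 3: size of the loss.** Take n = 242 Visit 4 attenders, an upper limit because 242 is the number enrolled. The percentage widening of the confidence interval (CI) does not depend on n.

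- Only an absent Visit 2 excludes: loss = n·p; CI width factor = 1/√(1 − p).
- An absent Visit 2 or Visit 3 excludes, each with probability p, independently: loss = n·[1 − (1 − p)²]; CI width factor = 1/(1 − p).

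| p (assumed) | Lost, Visit 2 only | CI wider | Lost, Visit 2 or 3 | CI wider |
|---|---|---|---|---|
| 5% | 242 × 0.05 = 12 | 2.6% | 242 × 0.0975 = 24 | 5.3% |
| 10% | 242 × 0.10 = 24 | 5.4% | 242 × 0.19 = 46 | 11.1% |
| 15% | 242 × 0.15 = 36 | 8.5% | 242 × 0.2775 = 67 | 17.6% |

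**Step 4: do the sensitivity analyses recover these patients?** They return, but with older values. Under LOCF, a patient without Visit 3 receives the Visit 2 value, which is the year-1 ARR. For a patient without Visit 2, the Visit 3 ARR also uses Visit 2 data; if an absent term voids that sum too, LOCF falls back to the Visit 1 value. BOCF substitutes the pre-baseline rate. Each sets aside follow-up that exists up to Visit 4.

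**The case against.** The strongest reply is that the practical reach is small. Visit 2 is where weight and cladribine intake are recorded (protocol 9.2.4), near the Year 2 course, so patients continuing treatment are unlikely to miss it. With no window on this endpoint, an early or late Visit 2 still counts. Absent patients reappear under LOCF and BOCF in the same table as the primary result, and SAP 10.1 tabulates attendance by visit. Much of this stands: the frequency may be low. But patients who stop treatment without changing drug stay in follow-up (protocol 9.2.5), tabulating attendance is not an analysis rule, and the sensitivity analyses replace observed data.

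A reader might also infer four stronger points that the documents do not support:

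- *An absent Visit 3 always excludes.* The SAP does not say so, and the days at risk remain known. It is an unspecified rule, not a demonstrated exclusion.
- *Year-2 ARR would be understated because a missing Visit 3 is read as zero.* That also requires the Visit 4 count to cover only the time since month 18. Protocol 9.2.4 asks for a running total, under which an unadjusted count would err upward, as in the 3.00 above.
- *Stable patients skip more, so the loss is selective.* This is plausible but undocumented. Losing stable patients would raise the year-2 ARR, not lower it.
- *A skipped visit is not a deviation.* SAP 10.2.1 says only that departures from the schedule are not important deviations.

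**Conclusion.** The point holds in two parts. A Visit 4 attender with no Visit 2 has no computable year-2 ARR and leaves the confirmatory comparison; this follows from the denominator and the complete-pairs rule read together. For an absent Visit 3 the SAP is silent, so the patient may be needlessly excluded or miscounted.

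The firm part costs 12, 24 or 36 of 242 patients at assumed Visit 2 absences of 5%, 10% or 15%. The upper range in Step 3 needs two further assumptions: exclusion for an absent Visit 3, and independent absences. No direction of bias is established. This is a modest loss of precision and an avoidable ambiguity in the primary endpoint, worth closing because the repair is cheap.

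**What to change.** Add to SAP 14.1.1, for patients with a Visit 4:

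1. State whether visit relapse counts are running totals, as protocol 9.2.4 describes, or per interval, and define the numerator to match.
2. If Visit 3 is absent, use all relapses between the Visit 2 and Visit 4 dates over those days (Visit 4 total minus Visit 2 total if counts are cumulative). Never read an absent count as zero.
3. If Visit 2 is absent, count relapses with onset in the 12 months before Visit 4. This matches the period in the protocol's primary endpoint. It uses relapse dates, assumed to be available because the fourth sensitivity analysis in SAP 14.3.2 needs time since relapse, or else a site query. Where neither works, use the Visit 3 to Visit 4 rate in a sensitivity analysis only: six months is 6 × 30.4375 = 182.6 days, so one relapse becomes 365.25/182.6 = 2.00 per year in an unweighted paired test.
4. Keep the strict version requiring Visits 2, 3 and 4 as a sensitivity analysis.

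The cost is a few lines of SAP text and programming and some site queries, settled before database lock. A patient missing both visits and without usable relapse dates stays missing.

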## **9** General Specifications for Data Analyses

This section describes any general specifications not included in subsequent sections. This study is a single cohort study and no comparison between groups is planned. The "start date" for this study is the start date of treatment with Cladribine.

Continuous variables will be summarized using descriptive statistics, i.e. the number of patients with non-missing values (n), the number of patients with missing values (nmiss), mean, standard deviation (SD), median, 25th percentile (Q1) and 75th percentile (Q3), minimum, and maximum. If there are no missing values, the number of patients with missing values (nmiss) should be indicated by a 0. Mean, median, Q1, Q3, minimum and maximum will be reported with the same number of decimal places as collected in raw data while SD will be reported with one extra decimal place.

Qualitative variables will be summarized by frequency counts and percentages. Unless otherwise stated the calculation of proportions will be based on the number of patients of the analysis set of interest. Therefore, counts of missing observations will be included in the denominator and presented as a separate category.

The overall significance level is 5% two-sided. Confirmatory statistical tests will be performed on the primary outcome only. All other statistical tests mentioned in this IAP are to be regarded as exploratory. Exploratory statistical tests comparing study treatment groups will be performed two-sided. If confidence intervals (CIs) are to be calculated, these will be two-sided with a confidence probability of 95%, unless otherwise specified in this IAP.

In order to provide overall estimates of treatment effects, data will be pooled across sites. The "site" factor will not be considered in statistical models or for subgroup analyses due to the high number of participating sites in contrast to the anticipated small number of patients treated at each site.

All analyses will be performed using SAS® Software version 9.4 or higher. R version 3.2.2 or higher may be used to create some of the figures in case it provides a better alternative layout.

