## 9.6 End of Study, Date of last Contact and Lost to Follow-up

End of study is defined as the last visit performed by the patient within the period of 24-Months  $\pm$  3 months after baseline.

A patient will be considered lost to follow-up when he/she prematurely discontinued the study, meaning that he/she discontinued the study prior to finalizing the 24-Months observational period. As per the protocol and eCRF options, a patient can be lost to follow-up due to:

- Withdrew consent from study
- Death
- Change to other DMD
- Other reason (e.g. not able to contact the patient)

As per the study design, discontinuation of treatment does not imply lost to follow-up. Patients who discontinue the treatment will continue to be followed for safety reasons until the 24-Months observational period ends or unless they switch to another DMD treatment.

The date of the last contact will be derived as:

- End of study date, for patients completing the observational period
- Date of death for patients lost to follow-up due to death
- Maximum of the following event dates, when complete dates available, for lost to follow-up patients when lost to follow-up cause is not death:
  - o Maximum available date of visit.
  - Study drug start
  - o Adverse Event (AE) start and end dates
  - o Concomitant Medication (CM) start and end dates
  - o Date of Quality of Life (QoL) questionnaires (MSIS-29, CCI and Treatment Satisfaction Questionnaire for Medication [TSQM]).

Only dates associated with patient actual examinations reported in the eCRF will be used in the derivation. Dates associated with a technical operation unrelated to patient status such as the date a blood sample was processed will not be used.

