## 14.2.1 Secondary Objective: Derivation and analysis of the Secondary Outcome ARR

#### **Derivations**

Pre-baseline ARR will be defined as the total number of relapses reported in the last 12 months prior to Cladribine treatment as collected in the "12 Month Historical MS Data".

Twelve month period after the start of Cladribine treatment ARR will be calculated as the sum of the number of MS relapses from Visit 1 and Visit 2 divided by the number of days between Visit 2 data and start date of Cladribine and multiplied by 365.25. If a patient discontinues the study prior to Visit 2, it will be set to missing and excluded from the primary analysis.

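### The signed-rank test sets a whole-number pre-baseline count against a day-rescaled post-baseline count, so a systematic drift in the Visit 2 to Visit 4 interval would take the only confirmatory test off its 5% level

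*SAP*

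**What the plan says.** SAP 14.1.1 builds the two halves of the comparison differently. For the first half, "Pre-baseline ARR will be defined as a total number of relapses reported in the last 12 months prior to Cladribine treatment", so the value is 0, 1, 2 and so on. For the second, the relapses reported at Visits 3 and 4 are summed and "divided by the number of days between Visit 4 date and Visit 2 date and multiplied by 365.25". The pair goes to repeated-measures ANOVA if Shapiro-Wilk does not reject. Otherwise: "In case the data is not normally distributed, Wilcoxon signed-rank test will be used instead".

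SAP Section 9 sets the level ("The overall significance level is 5% two-sided") and the status of the test: "Confirmatory statistical tests will be performed on the primary outcome only".

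On timing, SAP 9.5 aims Visits 2 and 4 at months 12 and 24 under routine care and adds: "Therefore, the timing of the visits is an approximation". Its day windows apply to patient-reported outcomes. The Modification History records that version 2.0 took windowing away for the primary and secondary endpoints. SAP 9.6 bounds the end: "End of study is defined as the last visit performed by the patient within the period of 24-Months", with a 3-month allowance either side. The sensitivity analyses in 14.1.2 (LOCF, BOCF) deal with missing data only.

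The year-1 analysis in 14.2.1 has the same structure, with the count "divided by the number of days between Visit 2 data and start date of Cladribine and multiplied by 365.25".

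**The concern.** Dividing by days at risk is the normal way to form a rate. The difficulty comes from ranking the difference between a rescaled count and one that was not rescaled. Two things happen:

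- **Ties break.** A patient with one relapse before and one after has difference 1 − 365.25/T, where T is the Visit 2 to Visit 4 interval in days. This is not zero for any whole number of days. A patient whose relapses did not change enters the test with a sign set by appointment dates.
- **Ranks shift.** A 1-to-0 patient always has absolute difference 1. A 0-to-1 patient has 365.25/T, which is below 1 when T is long and above 1 when T is short. Improvements and worsenings of one relapse should share a rank, but one group is moved ahead of the other.

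Both effects push the same way: long intervals towards a decrease, short intervals towards an increase. The error rate and power of the sole confirmatory test therefore depend on how clinics schedule visits.

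**Working it through.** **The plan's own figures.** The sample size of 242 cannot be reproduced, because its inputs are redacted. The other stated figure is the 5% two-sided level, which is what is checked here.

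**Mechanism by hand.** Take three patients, 1-to-1, 1-to-0 and 0-to-1, with difference = pre − post × 365.25/T.

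| T | Factor 365.25/T | 1-to-1 | 1-to-0 | 0-to-1 | Rank sum, decrease | Rank sum, increase |
|---|---|---|---|---|---|---|
| 365.25 | 1 | 0 (dropped) | +1 | −1 | 1.5 | 1.5 |
| 380 | 0.961 | +0.039 | +1 | −0.961 | 1 + 3 = 4 | 2 |
| 350 | 1.044 | −0.044 | +1 | −1.044 | 2 | 1 + 3 = 4 |

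The relapse counts are identical in all three rows.

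**Error rate when the relapse rate has not changed.** Pre-baseline counts are Poisson(λ) and post-baseline counts Poisson(λ × T/365.25). Some runs add gamma variation between patients (shape 2). The signed-rank test drops zeros, uses mid-ranks and a tie-corrected normal approximation, and is two-sided at 5%. The λ values and the interval distributions are assumptions, since the documents give neither. In the data sets checked, Shapiro-Wilk rejected every time, so the signed-rank branch is the one that will be used.

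At N = 242 (Poisson, 4,000 runs), with the SAP 9.5 questionnaire windows borrowed only to illustrate a spread:

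| Interval assumption | λ = 0.3 | λ = 0.5 | λ = 1.0 |
|---|---|---|---|
| No rescaling (365.25 days) | 4.6% | 4.8% | 4.6% |
| Visit 2 day 335–395, Visit 4 day 700–760 (mean 365) | 5.3% | 5.7% | 5.4% |
| Visit 4 in the late half, day 730–760 (mean 380) | 21.9% | 21.7% | 16.4% |
| Visit 4 in the early half, day 700–730 (mean 350) | 22.0% | 20.0% | 15.9% |
| Mean 395, SD 30 | 33.7% | 27.7% | 15.8% |

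The first row recovers the nominal 5%. Within those windows T runs from 700 − 395 = 305 to 760 − 335 = 425 days, so one relapse counts as 1.20 down to 0.86.

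At n = 200, mean ARR 0.3–1.0, with and without gamma variation, normal intervals:

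| Mean T (SD), days | Signed-rank rejection |
|---|---|
| 365–370 (30) | about 5–7% |
| 350 or 380 (30) | about 7–14% |
| 395 (30) | about 12–29% |
| 350 or 380 (14) | about 22–37% |

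For long intervals the false rejections are almost all decreases; for short ones, almost all increases.

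**Is it the test or the rescaling?** It is the combination. In the N = 242 runs, the paired mean test on the same rescaled values rejected in 4.1–5.8%, and a count model with log-days offset and robust variance in 4.3–6.0%, across all timing scenarios.

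**Why spread matters.** The inflation depends largely on how many intervals fall on one side of 365.25. At mean 380 and SD 14 the long share is Φ(14.75/14) = Φ(1.05) ≈ 85%. At SD 30 it is Φ(14.75/30) = Φ(0.49) ≈ 69%, and more of the broken ties cancel.

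**Power.** For a true 20% reduction (ARR 0.5, SD 30, n = 200), signed-rank power is about 15% at mean T 350 and 56% at mean T 380, against about 30% for a mean comparison. For a true 50% reduction (ARR 0.5, gamma variation, SD 30) it is 90%, 97% and 99.5% at mean T 350, 365 and 380.

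**The case against.** The strongest reply is that no document shows a drift. Visits 2 and 4 have month 12 and month 24 targets, and end of study is bounded to 24 ± 3 months. The instruction to record the appointment nearest the upper limit applies to both visits, so lateness common to both partly cancels in Visit 4 minus Visit 2. With wide, symmetric scatter the test is close to nominal. All of this stands. It limits the likely size, but it does not make the test's level independent of scheduling.

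Four stronger readings are tempting, and the documents do not support them:

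- **That one day decides the trial.** Take 200 patients, with 30 going 1 to 0, 30 going 0 to 1, 20 staying at 1 and 120 at 0. An interval of 366 days for everyone gives p = 0.007, with 50 relapses before and 50 after. But this needs identical intervals, and SAP 9.5 calls timing approximate. With intervals varying around 366 (SD 10 or SD 30), none of 1,000 draws reached p < 0.05.
- **That the primary result will be false.** If the true reduction is large, the test rejects under any of these timings. Sensitivity is material for moderate effects, and the assumed effect is redacted.
- **That dividing by days is wrong.** The endpoint is a rate, and a raw count ignores exposure.
- **That the year-1 test is a second confirmatory failure.** Its interval starts at the cladribine start date, so a late Visit 2 lengthens it with nothing to cancel. But SAP Section 9 makes it exploratory.

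**Conclusion.** The point holds as a conditional one and should be fixed. The mechanism follows from the SAP text alone: an unscaled count paired with a rescaled count, then ranked. Its size rests on assumed relapse rates and interval distributions. With intervals centred on one year and widely scattered, the error is about 5–7%. A 15-day mean shift gives about 7–14% at SD 30 and 22–37% at SD 14, and a 30-day lengthening at SD 30 gives 12–29%. Long intervals err in the direction that favours the product. Since version 2.0 removed windowing for this endpoint, the plan has month targets and an end-of-study bound, but nothing that centres the interval on 365.25 days and no analysis that would show whether the interval had affected the p-value.

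**What to change.** In SAP 14.1.1, make the primary test a Poisson log-link GEE with two records per patient: the pre-baseline count over 365.25 days, and the post-baseline count over the actual Visit 2 to Visit 4 days. Use log(days) as offset and robust standard errors clustered on patient. Report the rate ratio, 95% CI and p-value, alongside the mean ARR difference and its CI, because the endpoint is stated as a difference. Use the same model in 14.2.1 (exploratory) and in 14.1.2, where each carried-forward count should keep its own days.

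If a signed-rank p-value is kept, make it supportive only and compute it on whole-count differences, so that equal counts tie at zero. State its limits: it ignores exposure differences and can itself exceed 5% when intervals are long (up to 12% at mean ARR 1.0 and mean T 395).

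The cost is SAP wording and a few lines of SAS, with no new data. Protocol 9.7.3 names ANOVA or Wilcoxon, and SAP Section 7 declares no departures from the protocol, so the change must be recorded there before database lock.

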9.2.5 Withdrawal from the Study

Patients may discontinue from the study at any time (withdraw consent). The reason for any study discontinuations will be collected, if available.

Patients who discontinue treatment will continue to be followed until end of follow-up period regardless of treatment status, unless they switch to another DMD treatment in which case they should be withdrawn from the study.

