## 14.1.2 Sensitivity Analyses of the Primary Outcome ARR

A sensitivity analysis will be conducted using two different methods for missing data imputation, to assess the robustness of the primary analysis described above.

The first method will include a Last Observation Carried Forward (LOCF) approach, for which the last available ARR from previous visits will be used for the analysis.

The second method will include a Baseline Observation Carried Forward (BOCF) for which missing data for post-baseline ARR will be imputed as the pre-baseline ARR.

Both summary statistics and statistical results will be presented in the same table as the primary analysis. These sensitivity analyses are considered as supportive of the primary analysis.

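### The confirmatory year-2 relapse-rate comparison drops everyone who leaves before Visit 4, DMD switchers included, and no planned ARR analysis uses all observed relapse time; the relapse-count definition also differs between protocol and SAP

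*SAP*

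**What the plan says.** SAP 9 makes the primary outcome the only confirmatory test, at 5% two-sided. Under SAP 14.1.1 the pre-baseline ARR is the relapse count in the 12 months before cladribine. The year-2 ARR adds the Visit 3 and Visit 4 counts, divides by the days from Visit 2 to Visit 4 and multiplies by 365.25. For early leavers: "If a patient discontinues the study prior to Visit 4, it will be set to missing and excluded from the primary analysis". The analysis methods repeat this: "Patients with missing data at one or both time points will not be included in the analysis".

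Protocol 9.2.5 keeps following patients who stop cladribine, "unless they switch to another DMD treatment in which case they should be withdrawn from the study". SAP 9.6 lists "Change to other DMD" among the reasons for loss to follow-up.

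SAP 14.1.2 plans two imputations. Under LOCF "the last available ARR from previous visits will be used for the analysis"; under BOCF "missing data for post-baseline ARR will be imputed as the pre-baseline ARR". For earlier visits the SAP says "For other study visits, ARR will be calculated similarly including data from the last 2 visits", so a patient who leaves after Visit 3 carries forward roughly months 6 to 18. A further table summarises the results by visit, "including ARR at each visit and absolute and relative change from baseline", and SAP 9.1 defines percent change patient by patient.

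Protocol 9.2.4 asks at each follow-up visit for the patient's relapse total in the study to date. It also asks for a relapse total at early termination, if available.

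**The concern.** The objective concerns patients who switch to cladribine, but the result describes those who reach Visit 4. A patient who relapses in year 2 and is moved to another DMD takes both the pre-baseline count and the year-2 relapses out of the comparison, so missingness may depend on the outcome itself.

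Neither imputation repairs this. LOCF misses any relapse after the last attended visit, which may be the one that led to the switch. If the switch waits for the next visit, LOCF instead carries forward a window selected for containing a relapse. BOCF assumes no change. The termination total is requested, but the ARR derivation gives it no role. What is at stake is the size of the reported effect.

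The second matter is one of definition. If sites enter running totals, as Protocol 9.2.4 words it, the SAP's sum counts the same relapses twice and includes relapses from year 1.

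**Working it through.** **Precision.** The documents give N = 242. The sample-size assumptions are not visible, and no switch rate is given, so N cannot be reproduced. For a paired comparison at 80% power, detectable difference/SD = (1.960 + 0.842)/sqrt(N): 0.180 at 242, and 0.201 at 194 (20% lost). Precision suffers little; the question is bias.

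**Assumptions (none from the documents).** Pre-baseline ARR 1.0 or 1.5; post-baseline ARR 0.2 or 0.3; gamma-Poisson relapses with dispersion 1.0; pre/post correlation of patients' rates 0, 0.5 or 1; 5, 15 or 30% of relapses leading to withdrawal; 4% yearly unrelated loss; switch at once or at the next visit. That is 72 scenarios of 200,000 simulated patients.

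**Why the difference can err either way.** A separate, simpler run (pre-baseline ARR 1.0, post-baseline 0.20, 25% of relapses leading to withdrawal about a month later, 5% yearly other loss) shows the mechanism. Differences are taken before rounding.

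| | True difference | Completers: pre, year 2, difference | Relative reduction, true / completers |
|---|---|---|---|
| Same rate for all patients | 0.802 | 1.003, 0.154, 0.849 (+6%) | 80.1% / 84.7% |
| Patients' rates vary, shared by both periods | 0.800 | 0.910, 0.139, 0.770 (-4%) | 80.0% / 84.7% |

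The completers' year-2 ARR is too low in both rows. In the second row their pre-baseline ARR is too low as well, and the error in the difference changes sign.

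**Full grid, 15-30% of relapses leading to withdrawal.** True means the year-2 rate had nobody withdrawn, unless stated.

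| | Switch at once | Switch at next visit |
|---|---|---|
| Reach Visit 4 | 78-87% (189-211 of 242) | 81-88% (196-214 of 242) |
| Completers' year-2 ARR / true | 0.59-0.81 | 0.74-0.89 |
| Completers' year-2 ARR / rate observed on study | 0.67-0.84 | 0.83-0.92 |
| Error in difference, completers | -9% to +17% | -9% to +11% |
| Relative reduction overstated (ratio of means) | 2-12 points | 0.9-7.7 points |
| Error in difference, LOCF | +0.5% to +12% | -16% to -3% |
| Error in difference, BOCF | -29% to -7% | -26% to -9% |

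At 5%, over both timings, the ratio to true is 0.92-0.96, the error in the difference -2% to +4%, and the overstatement 0.3-2.4 points.

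**The SAP's own relative change.** Computed per patient as in SAP 9.1, the overstatement at 15-30% is 1.1-8.8 points. It is undefined for patients with no pre-baseline relapse: 1/(1 + ARR) of patients at dispersion 1.0, so 1/2.0 = 50% or 1/2.5 = 40%.

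**The test.** For a paired comparison of means, expected z = completers' mean difference / (SD / sqrt(242 x completion)) is 6.8-10.4, against a critical value of 1.96.

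**Count conflict.** At a constant yearly rate r, running totals are 1.5r at Visit 3 and 2.0r at Visit 4. Their sum over one year is 3.5r, against a true r. Visit 4 minus Visit 2 gives 2.0r - 1.0r = r.

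**The case against.** - **The endpoint is not shown to be inflated.** A reader might infer that the plan flatters its primary result or endangers the test. The documents support neither. At 15-30%, completers understate the difference in 22 of 48 scenarios, and the error is under 5% in 31 of 48. In all 72 it is smaller than the half-width of the 95% CI (19-29% of the difference). This stands. Against it, the completers' CI covered the true difference in only 83-93% of trials, though in just four simulated scenarios.
- **The completer derivation follows the endpoint.** The window ends at End of Study, which SAP 9.6 places at 24 months plus or minus 3, and an early leaver has no such window. This stands in part: the shortfall depends on the benchmark and is smaller against the on-study rate.
- **Attrition is already handled.** LOCF and BOCF are planned, SAP 10.1 tabulates reasons for leaving, Protocol 9.9 names attrition, and the by-visit and 1-year results use leavers' earlier data. All true. But a reader might infer that LOCF and BOCF bracket the truth. At 15-30% they did so in 24 of 24 scenarios with switching at once (9 of 24 if LOCF gives patients without Visit 1 their baseline ARR), and in 0 of 24 with switching at the next visit. Nor is BOCF a guaranteed lower bound: with 10% withdrawn at a rate of 1.5, completers at 0.15 and pre-baseline 1.0, the true difference is 1 - (0.9 x 0.15 + 0.1 x 1.5) = 0.715, while BOCF gives 0.9 x 0.85 = 0.765.
- **The SAP breaks the protocol's censoring rule.** This is a tempting inference, because Protocol 9.2.4 speaks of censoring patients lost to follow-up. The same sentence leaves the handling to the SAP, so it is loose wording.
- **The remedy is fragile.** It needs termination counts that are collected only if available. This stands and is costed below.

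**Conclusion.** The concern holds as a gap in the supportive analyses. The completers' year-2 ARR understates the whole-FAS rate if relapses prompt switching. The size rests on an assumed switch rate: material at 15-30% of relapses, small at 5%. The absolute difference has no fixed direction of error, and the primary test can stay. LOCF's bias changes sign with the timing of switching, which the plan cannot know in advance, so the two imputations do not locate the effect. At 15-30% the relative reduction is overstated by about 1-12 points as a ratio of means, or 1-9 points as SAP 9.1 defines it.

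The count conflict needs none of these assumptions. A reader might infer that the year-2 ARR will be 3.5 times too high. That follows only if the eCRF holds running totals and the relapse rate is constant; on the first, the documents disagree and do not settle it.

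**What to change.** 1. Reconcile Protocol 9.2.4 with SAP 14.1.1 before lock. If counts are cumulative, define year-2 relapses as the Visit 4 count minus the Visit 2 count.
2. Keep the primary test. Add to SAP 14.1.2 one supportive analysis of all FAS patients with any post-baseline relapse count: a shared-frailty negative binomial model with log(days) offset and periods pre-baseline, year 1 and year 2. Include leavers' relapses up to the date of their last count. Report the rate ratio and the marginal rate difference with 95% CIs, and state how the difference is derived. Name one target, the rate while on study and not switched to another DMD, and judge every method against it. Say what LOCF does for patients without Visit 1.
3. Query sites for termination relapse counts, and tabulate leavers with and without them against completers by pre-baseline ARR.

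The cost is SAP text, one model, one small table and site queries. Nothing is imputed, in line with Protocol 9.7.2. The model relies on switching depending on observed relapses, and it extrapolates year 2 for patients who leave in year 1. At 15-30%, against the rate had nobody withdrawn, its error in the difference was -0.2% to +3.1% with all termination counts. With switching at once it was +0.5% to +10% with half of them missing (closer than completers in 15 of 24 scenarios) and +0.9% to +16% with all missing (12 of 24).
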